5.4. Subject Disposition

The following summaries by table will be provided:

- The total number of screened patients
- The total number of randomized patients: received a randomization number
- The total number of patients in each analysis set
- The total number of patients who completed the study and discontinued the study with the reason of discontinuation
- The total number of patients who completed the study treatment and discontinued the study treatment with the reason of discontinuation
- The total number of patients who continued in pediatric open label extension study
- The total number of patients who entered into follow-up period and their study completion status with reason of discontinuation
- The total number of patients potentially unblinded

The following listings will be provided:

- Listing of patient disposition including: date of randomization, date of the last visit, received dose, completed study drug or discontinued by reason, completed study or discontinued by reason
- A listing of patients randomized but not treated, and patients randomized but not treated as randomized
- A listing of patients prematurely discontinued from the study or treatment, along with reasons for discontinuation
- Summary table with listing of protocol deviations will be provided
- A listing of patients potentially unblinded

5.5. Dose administration

The compliance with study treatment will be calculated as follows:

Treatment Compliance= (Number of study drug injections during exposure period) / (Number of planned study drug injections during exposure period) x 100%

Summary of study drug administration will include the number of study drug doses administered and treatment compliance. The treatment compliance will be presented by the following specific ranges for each treatment group: <80%, and ≥80%.

Listing of dose administration: including date/time, study day, number of injections, locations of injections, dosing information, and whether or not the total dose is administered for each dose will be presented.

5.6. Treatment Exposure and Observation Period

The duration of treatment exposure during the study in day is calculated as:

Q2W dosing: (Date of last study drug injection – date of first study drug injection) + 14 days

Q4W dosing: (Date of last study drug injection – date of first study drug injection) + 28 days

The calculations are regardless of temporary dosing interruption. The duration of exposure during the study will be summarized by treatment group using number of patients, means, SD, minimums, Q1, medians, Q3 and maximums.

In addition, the duration of exposure will be summarized categorically by counts and percentages for each of the following categories and cumulatively by these categories as well: ≥ 14 days, ≥ 28 days, ≥ 42 days, ≥ 56 days, ≥ 70 days, ≥ 84 days, ≥ 98 days, and ≥ 112 days.

The duration of observation period during the study in day is calculated as:

(Date of the last visit – date of the first study drug injection) + 1.

The number (%) of patients with observation periods will be presented by specific time periods. The time periods of interest is specified as: < 8 days, ≥ 8 days, ≥ 15 days, ≥ 22 days, ≥ 29 days, ≥ 50 days, ≥ 57 days, ≥ 85 days, ≥ 99 days, ≥ 113 days, ≥ 141 days, ≥ 169 days, ≥ 183 days and ≥ 197 days.

5.7. Analyses of Efficacy Variables

For all efficacy variables, the analysis will be comparisons of each dupilumab regimen and the placebo treatment groups. The following null and alternative hypotheses for the primary endpoint will be tested for each dupilumab regimen group and the placebo group:

H0: $p_{dupilumab} = p_{placebo}$, where p stands for the percent of responders in a treatment group

H1: $p_{dupilumab} \neq p_{placebo}$.

The analyses of efficacy variables are described in the subsections below and summarized in [Appendix 10.1](#).

Subgroups are defined by key baseline factors recorded on the CRF and listed to be considered for primary and key secondary efficacy analyses:

- Age group (≥ 6 to < 9 , ≥ 9 to < 12)
- Sex (Male, Female)
- Ethnicity: Hispanic or Latino (no/yes)
- Race (White, Black or African American, Asian, Other)
- Duration of AD (< 5 years, ≥ 5 years)
- Age of disease onset (< 2 years, ≥ 2 years)

- Age of disease onset (<5 years, ≥5 years)
- Family history of atopic disease (Yes/No)
- Baseline weight group (<30 kg, ≥30 kg)
- BMI (<20, ≥20)
- Region (North America, Europe)
- Baseline severe EASI (<25, ≥25)
- Baseline moderate-to-severe EASI (<20, ≥20)
- Baseline worst itch scale (<7, ≥7)
- Body Surface Area (BSA) (≥10%-<30%, ≥30%-<50%, ≥50%)
- Baseline SCORAD score (<50, ≥50)
- Previous usage of ciclosporin (CsA) (Yes, No)
- Previous usage of methotrexate (MTX) (Yes, No)
- Previous usage of Azathioprine (Aza) (Yes, No)
- Previous use of systemic immunosuppressants for AD (Yes, No)
- History of asthma (Yes, No)
- History of nasal polys (Yes, No)
- History of allergic rhinitis (Yes, No)
- History of food allergies (Yes, No)

5.7.1. Analysis of Primary Efficacy Variable

The Cochran-Mantel-Haenszel (CMH) test adjusted by randomization strata (baseline weight group (<30 kg or ≥30kg) and region (North America or Europe) will be used for the analysis of percentage of patients with IGA 0 or 1 at week 16 or percentage of patients with EASI-75 at week 16. The Mantel-Fleiss (MF) criterion will be performed, and if it is not met while using the option CMH (MF) in SAS procedure PROC PREQ, sensitivity analyses including each factor separately in CMH test will be conducted.

All efficacy data, regardless of whether the patient remains on study treatment or discontinues the study treatment but remains in the study, will be used for analysis. Specifically, if a patient stays in the study until the end of the study planned placebo-controlled treatment period, all efficacy data collected up to the study planned end of treatment visit will be included in the primary analysis, regardless of whether the patient is on treatment or not.

Handling of dropouts or adjudicated rescue treatment or missing value for the binary response variables as the primary analysis

- If a patient withdraws from the study, this patient will be counted as a non-responder for the time points after withdrawal.
- To account for the impact of rescue treatment on the efficacy effect: if rescue treatment is used (see Section 4.3 for rescue treatment), the patient will be specified as a non-responder from the time the rescue treatment is used.
- If the patient has the missing value at week 16, then it will be counted as a non-responder at week 16.

Sensitivity analyses

1. Post-baseline Last Observation Carried Forward (LOCF) approach after censoring for rescue treatment use or study withdrawal to determine patient's status at week 16 will be conducted to assess the robustness of the primary efficacy analysis with regards to handling of missing data.
2. All observed data, regardless if rescue treatment is used or data is collected after withdrawal from study treatment will be included for analysis. Patients with missing value will be counted as non-responder.

The primary efficacy analyses will be performed on the FAS, which will be considered as the primary analysis. Evaluation of primary and co-primary endpoints in the mFAS and PPS will be considered as sensitivity analyses.

5.7.2. Analyses of Secondary Efficacy Variables

All secondary endpoints will be evaluated on the FAS. Selected secondary endpoints will be evaluated in the mFAS as sensitivity analyses.

The binary secondary efficacy endpoints will be analyzed using the same approaches used for the analysis of the primary endpoints.

The continuous endpoints will be analyzed using analysis of covariance (ANCOVA) model as the primary analysis method with multiple imputation (MI) method for missing data. Patients' efficacy data through week 16 after the rescue treatment use will be set to missing first, and then be imputed by MI method. To account for the uncertainty in the imputation, missing data from the FAS will be imputed 40 times to generate 40 complete data sets by using the SAS procedure MI following the 2 steps below:

Step 1: The monotone missing pattern is induced by Markov Chain Monte Carlo (MCMC) method in MI procedure using seed number 12345. The monotone missing pattern means that if a patient has missing value for a variable at a visit, then the values at all subsequent visits for the same variable are all missing for the patient.

Step 2: The missing data at subsequent visits will be imputed using the regression method for the monotone pattern with seed number 54321 and adjustment for covariates including treatment groups, randomization strata (baseline weight group and region), and relevant baseline.

Once imputations are made, the week 16 data of each of the 40 complete datasets will be analyzed using ANCOVA model with treatment, randomization strata (baseline weight group and region), and relevant baseline included in the model, and the SAS MIANALYZE procedure will be used to generate valid statistical inferences by combining results from the 40 analyses using Rubin's formula.

The imputation model will include:

- The covariates included in the ANCOVA model, including the treatment group, the baseline value and the randomization strata (baseline weight group and region)
- Measured endpoint values at every clinic visit (i.e. week 1, 2, 3, 4, 8, 12 and week 16)

Categorical variables included in above model (i.e., treatment group and randomization strata) are not expected to be missing.

To account for the impact of rescue treatment on the efficacy effect:

- Continuous efficacy endpoints: if a patient receives rescue treatment that specifies the patient as a non-responder according to the above rules for binary efficacy endpoints, the data collected after rescue treatment is initiated will be treated as missing.

Sensitivity analyses

In addition to the MI method described previously, sensitivity analyses for the continuous endpoints for EASI and/or Pruritus worst itch scale will be conducted as described below.

1. The sensitivity analysis based on all observed data regardless if rescue treatment is used or data is collected after withdrawal from study treatment using MI method will be performed.
2. This sensitivity analysis will use ANCOVA model, including the treatment group, the baseline value and the randomization strata. The efficacy data will be set to missing after rescue treatment is used. The post-baseline LOCF method will then be used to impute missing values.
3. This sensitivity analysis will use ANCOVA model, including the treatment group, the baseline value and the randomization strata. The efficacy data will be set to missing after rescue treatment is used. The post-baseline worst observation carried forward (WOCF) method will then be used to impute missing values.

Time to onset of effect on pruritus as measured by proportion of patients with improvement (reduction) of weekly average of daily Pruritus worst itch scale ≥ 4 and ≥ 3 from baseline during the 16-week treatment period will be calculated for each patient as the date of having the first event - the first study drug dose date + 1 day. Patients not having either event during the treatment period will have their time censored at the end of treatment period. These times to onset of effect on pruritus will be analyzed using the Cox proportional hazards model including treatment and randomization strata as factors, The hazards ratio, its 95% confidence interval and p-value will be reported. Kaplan-Meier curves will be provided.

The mean weekly dose of TCS use during the treatment period endpoints will be analyzed using an ANCOVA model with treatment, randomization strata (baseline weight group and region) and relevant baseline included in the model.

Analysis of incidence of TEAE-related variables

- Incidence of skin infection TEAE (excluding herpetic infections) from baseline through week 16
- Incidence of treatment-emergent serious adverse events from baseline through week 16

These endpoints will be analyzed for patient in SAF. The week 16 treatment period is defined in Section 3.2. The Cochran-Mantel-Haenszel test adjusted for randomization strata will be used for the percentage of patients with events described above through week 16.

Multiplicity Considerations

The following multiplicity adjustment approach, a hierarchical procedure, will be used to control the overall Type-1 error rate at 0.05 for the primary endpoint and the secondary endpoints across the 2 dupilumab dose regimens versus placebo. Each hypothesis will be formally tested only if the preceding one is significant at the 2-sided 0.05 significance level. The hierarchical testing order is shown in below table (all comparisons are with the placebo).

		Dupilumab	
Endpoints		q4w group	q2w group
Primary endpoint	Proportion of patients with IGA 0 to 1 (on a 5-point scale) at week 16	7	1
Co-primary endpoint for EMA and EMA Reference Market Countries only, key secondary for US	Proportion of patients with EASI-75 ($\geq 75\%$ improvement from baseline) at week 16	8	2
Secondary endpoints	Percent change in EASI score from baseline to week 16	9	3
	Proportion of patients with EASI-50 at week 16	10	4
	Percent change from baseline to week 16 in weekly average of daily worst itch score	11	5
	Proportion of patients with improvement (reduction) of weekly average of daily worst itch score ≥ 4 from baseline at week 16	12	6
	Proportion of patients with improvement (reduction) of weekly average of daily worst itch score ≥ 3 from baseline at week 16	15	13
	Proportion of patients with EASI-90 at week 16	16	14
	Change from baseline to week 16 in POEM	20	17
	Change from baseline to week 16 in CDLQI	21	18
	Percent change from baseline to week 16 in SCORAD	22	19

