5.7.3. Subgroup Analysis

Subgroup for the primary endpoint and key secondary efficacy will be analyzed based on FAS. The analysis method for the subgroup will be the same as the primary analysis described in Section 5.7.1 and Section 5.7.2. Interactions between the subgroups and treatment groups will also be tested using the logistic regression model for the categorical endpoints, and using the ANCOVA model for the continuous endpoints. The model will include randomization strata, treatment group, subgroup, treatment by randomization strata interaction and treatment by subgroup interaction as factors. P-values for the interaction term will be reported. We will consider interaction effect as significant if P-value is greater than 0.1.

Forest plots of the primary and key secondary efficacy endpoints across subgroups will be generated.

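### The imputation model for continuous endpoints omits every treatment-by-subgroup term, so the interaction results for percent change in EASI and itch can be biased; a cheap fix of low to moderate priority

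*SAP*

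**What the plan says.** SAP 5.7.2 analyses continuous endpoints by ANCOVA after multiple imputation. A patient's "efficacy data through week 16 after the rescue treatment use will be set to missing first", and then "missing data from the FAS will be imputed 40 times to generate 40 complete data sets". The imputation model has two groups of terms: "The covariates included in the ANCOVA model, including the treatment group, the baseline value and the randomization strata (baseline weight group and region"), and "Measured endpoint values at every clinic visit (i.e. week 1, 2, 3, 4, 8, 12 and week 16"). No product term is named.

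SAP 5.7.3 covers the subgroup analyses. It says "The analysis method for the subgroup will be the same as the primary analysis described in Section 5.7.1 and Section 5.7.2". For the interaction tests on continuous endpoints it specifies an ANCOVA: "The model will include randomization strata, treatment group, subgroup, treatment by randomization strata interaction and treatment by subgroup interaction as factors". Interaction p-values and forest plots are to be reported. Appendix 10.1 confirms that percent change in EASI and percent change in worst itch both receive subgroup analysis.

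SAP 5.7 lists 24 subgroup factors, among them "Baseline weight group (<30 kg, ≥30 kg") and region.

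**The concern.** Imputed values can only carry the structure that the imputation model allows. Here the analysis model contains treatment-by-subgroup and treatment-by-strata terms, and the imputation model contains neither. A child whose week-16 value is imputed receives the treatment effect averaged over subgroups, apart from what that child's own earlier visits reveal. For most factors the subgroup's own main effect is missing as well.

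The missing share is plausibly unequal between arms. Protocol 7.3 allows rescue at IGA 4 or for intolerable symptoms, every child enters at IGA 4 (Protocol 6.2.1), and Protocol 10.2 assumes EASI-75 in 17% on placebo against 62-68% on dupilumab.

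What is at stake is the forest plots and interaction p-values for two continuous key secondary endpoints. Weight group is the factor that readers will look at most. The Q4W dose is the same at every weight, and Protocol 3.2.2 describes exposure as falling with body weight.

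**Working it through.** **The plan's own figure.** The only design calculation is the power table (Protocol 10.2, SAP 2.2): 97% and 87% for IGA 0/1, and 99% twice for EASI-75, at 80 per group. A pooled chi-square calculation gives 98.0%, 89.0% and above 99.9% for both EASI-75 comparisons; Fisher's exact test gives 97.9% and 87.2% for IGA. The table reproduces to within 2 points, but it says nothing about missing data or subgroups.

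**Coverage of the 24 factors.** Weight group and region enter as main effects. For the EASI endpoint the baseline value partly covers the two baseline-EASI splits, which leaves 24 - 2 - 2 = 20 factors with no term. For itch it partly covers one split, which leaves 24 - 2 - 1 = 21. None of the 24 has an interaction with treatment.

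**Simulation set-up.** From the SAP: regression imputation of monotone missing data at weeks 1, 2, 3, 4, 8, 12 and 16, with treatment, weight group, region and baseline as covariates, followed by ANCOVA with treatment-by-subgroup terms. Assumed, because the documents give no values: residual SD 30 points, correlation 0.6 to 0.9 per 4 weeks, data missing at random, two time courses for the subgroup difference, and the missing rates shown. The MCMC step that makes the pattern monotone was not simulated.

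Share retained = interaction after imputation / interaction on full data. Example (correlation 0.8, heaviest missingness): 13.04 / 14.80 = 0.881, a shrinkage of 1 - 0.881 = 12%. The lowest value with the subgroup absent was 12.56 / 15.21 = 0.826.

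Large-sample results (N = 300,000). The two middle columns have a true interaction of -15 points. The last has none, but the subgroup shifts the outcome by 15 points in every arm.

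| Missing at week 16, placebo / dupilumab | Retained, subgroup absent | Retained, main effect only (weight, region) | False interaction, subgroup absent |
|---|---|---|---|
| about 6% / 4% | 0.95-0.98 | not run | about 0.2 points |
| 25% / 4% | 0.96-0.99 | 0.85-0.88 | 1.5-2.4 |
| 36% / 8% | 0.92-0.95 | 0.77-0.82 | 2.0-3.2 |
| 57% / 16% | 0.83-0.91 | 0.60-0.68 | 3.0-4.9 |

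A main effect alone does worse than no term in these runs because it spreads the subgroup difference over all arms, so imputed placebo children receive a difference that belongs to dupilumab. With the subgroup and its interaction in the imputation model, the true -15 came back at about -14.5 to -15.4, within about 0.4 points of full data. The false interaction in the last column disappears once the subgroup's main effect is imputed.

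**Which arm carries the difference.** A second simulation used 110 per arm, a 20-point interaction, correlation 0.75 and the subgroup absent from the imputation. At 20/5%, 30/10% and 40/15% missing it retained 0.958, 0.925 and 0.884 when the difference lay in the dupilumab arm, and 0.845, 0.772 and 0.688 when it lay in the placebo arm. With the terms added, 0.997 to 1.010 was retained.

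**At the trial's size.** N = 330, 40 imputations, 250 simulated trials, interaction tested at 0.10:

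| Truth | Missing | Mean estimate: plan / with terms | Rejection rate: plan / with terms / full data |
|---|---|---|---|
| interaction -20 | 25% / 4% | -18.6 / -18.9 | 0.68 / 0.70 / 0.73 |
| interaction -20 | 57% / 16% | -17.2 / -19.2 | 0.59 / 0.60 / 0.79 |
| none | 25% / 4% | 0.0 / 0.0 | 0.07 / 0.12 / 0.12 |
| none | 57% / 16% | 0.4 / 0.7 | 0.01 / 0.08 / 0.07 |
| none, prognostic subgroup | 25% / 4% | 1.8 / -0.3 | 0.10 / 0.12 / 0.13 |
| none, prognostic subgroup | 57% / 16% | 4.1 / 0.0 | 0.03 / 0.09 / 0.11 |

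Monte Carlo error on a rate near 0.68 is sqrt(0.68 x 0.32 / 250) = 0.03. The estimate's standard error under the plan was about 9.7 in the second row. The bias there against full data (-19.58) is (19.58 - 17.25) / 9.70 = 0.24 standard errors.

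The 0.10 level was read as p below 0.1. SAP 5.7.3 prints the reverse ("We will consider interaction effect as significant if P-value is greater than 0.1"), which is a separate error to correct.

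**The case against.** The strongest reply is that SAP 5.7.3 sends the subgroup analysis back to the methods of 5.7.2, and those methods include the imputation. If the imputation is rerun within each subgroup, the subgroup estimates are not pushed together. This stands in part. SAP 5.7.3 does not say which reading is meant, although 5.7.2 describes one imputation of the whole FAS. The interaction test pools the subgroup levels and still needs imputations that allow for the interaction.

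Four stronger readings are tempting, and the documents or the check do not support them:

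- *The imputation model contains no subgroup term at all.* Weight group and region are in it as main effects, and the baseline value partly serves the baseline-EASI and baseline-itch splits.
- *Results are always drawn toward no difference.* A prognostic subgroup with unequal missingness produces the opposite.
- *The interaction tests lose power by construction.* At 330 patients the gaps were 0.68 against 0.70 and 0.59 against 0.60, inside simulation error. What did show was a test too conservative under heavy missingness (0.01 at a nominal 0.10).
- *The trial's main conclusions are at risk.* The FAS treatment comparisons do not use these terms, subgroups lie outside the hierarchy in SAP 5.7.2, and the binary subgroup analyses count rescued or missing patients as non-responders.

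It is also fair that the larger figures depend on assumed rates or on where the difference lies, and that weight-tiered Q2W dosing was meant to give similar mean exposure in both weight groups (Protocol 3.2.2). That weakens weight as an example for Q2W, but not for Q4W.

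**Conclusion.** The mismatch is plain in the text, and its consequence is conditional. If the single FAS imputation feeds SAP 5.7.3, interaction estimates for percent change in EASI and itch are biased. With few missing values the loss is a few percent. With heavy missingness, or for weight group and region, it is about 10-40%. A false interaction of a few points is possible where a prognostic subgroup meets unequal missingness.

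These sizes rest on assumed missing rates, an SD of 30 points and data missing at random. At the trial's size the bias is well below one standard error, so it distorts forest plots and test calibration more than it changes decisions. The affected outputs are exploratory. This is a worthwhile improvement of low to moderate priority.

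**What to change.** In SAP 5.7.3:

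- State which imputed data sets feed the subgroup estimates and the interaction tests.
- For continuous endpoints, rerun the imputation for each subgroup factor with that factor and its interaction with treatment added to both imputation steps. For weight group and region, add only treatment-by-stratum.
- Apply this only where every treatment-by-subgroup cell has enough patients, with the minimum stated in advance. Collapse or omit sparse or empty levels. Baseline EASI below 20 should be empty, because Protocol 6.2.1 requires at least 21.
- Leave the main FAS imputation unchanged and use it for the overall row of each forest plot.

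The cost is SAP wording and computing: at most 24 factors x 2 endpoints = 48 reruns. Imputations become more variable in small subgroups. Each factor's rows also rest on their own imputed data, so they need not average exactly to the overall row; a footnote should say so.
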